10.6.2 General allergic adverse events

Specific e-CRF screens are to be filled in to assess allergic AEs or allergic-like AE that may occur during the clinical studies conducted with alirocumab. Sometimes transient injection site reactions, irritant in nature, may occur, requiring no intervention and being of dubious significance. These reactions would not be considered to be allergic reactions. Adverse events that may constitute an allergic reaction (eg, generalized itch, nasal itch, swelling at injection site, flushing, hives, swelling at lips, eyes, face, tongue, hands, feet, lump in throat, difficulty to swallow, hoarseness, change in pitch of voice, incapacity to speak, wheezing, chest tightness, stridor, etc) should be considered to be reported on the General Allergic Event and/or Local Injection Site Reaction Complementary Form.

Adverse events that are obviously not of allergic origin (eg, LISR related to mechanics of injection) should only be recorded on the Local Injection Site Reaction Complementary Form. However, injection site reactions that progress/expand/worsen/etc should be evaluated as recommended in [Appendix G](#) and General Allergic Reaction Complementary form should be completed.

The IMP should be immediately interrupted (temporarily discontinued) if there is a suspicion of an allergic event related to IMP. See [Section 10.3.1](#) for further information on treatment interruption and [Section 10.3.3](#) for criteria for permanent treatment discontinuation.

10.6.2.1 Allergic adverse event with cutaneous involvement

Adverse events with cutaneous involvement which are obviously of allergic origin or injection site reactions which progress/expand/worsen/etc. should be evaluated by a dermatologist as soon as possible, and preferably within one week of the site first becoming aware of the event.

The Investigator should evaluate the patient for possible etiologies (new medications, etc) and extracutaneous symptoms and signs. An unscheduled assessment for hematology, chemistry, liver panel, and PK should be obtained. An additional blood sample will have to be drawn for anti-alirocumab antibody analyses (adequate instructions will be provided to the site by the Monitor). If it is possible, the site will take pictures of the skin lesions in order to provide the patient with them for the dermatologist's visit. If the photos are obtained, then copies should be kept as source documents which may later be collected by the sponsor. The Investigator will provide a summary of the patient's case, reason for consultation, and information being requested to the consulting dermatologist.

A full consultation report should be sent by the dermatologist to the Investigator. The full report should contain, at a minimum, the following information; a detailed description of the rash (such as the morphology [lesion type], shape of individual lesions, arrangement of multiple lesions [eg, scattered, grouped, linear], distribution, color, consistency, presence of pruritus or pain, and other clinical signs) and in case a skin biopsy (including histopathology and immunofluorescence) was done (if it was deemed necessary as per the dermatologist's or Investigator's medical judgment), the results of this investigation with, if applicable, a specific diagnosis of the AE. The Investigator will fax the full report and the corrected AE form if necessary, to the Monitoring Team Representative within 24 hours.

10.6.2.2 Acute allergic injection reactions

Acute allergic injection reaction (which are considered under the category of general allergic events) is defined as any AE that occurs during or shortly after injection of the IMP (characterized by but not limited to hypotension, bronchoconstriction, urticaria, edema, angioedema, nausea, vomiting). Emergency equipment and medication for the treatment of these potential adverse effects (eg, antihistamines, bronchodilators, IV saline, corticosteroids, acetaminophen, and epinephrine) must be available for immediate use for the injections at the training, and inclusion visits. Patients will be observed at the investigational site for at least 30 minutes following the injection that takes place at the inclusion visit. Patients should be treated symptomatically if any AEs are observed. Patients are to remain at the site until any acute injection reaction is assessed as stable, per the Investigator's discretion.

A General Allergic Event and/or Local Injection Site Reaction Complementary Form will have to be completed.

10.7 ADVERSE EVENTS MONITORING

All events will be managed and reported in compliance with all applicable regulations, and included in the final clinical study report.

11 STATISTICAL CONSIDERATIONS

11.1 DETERMINATION OF SAMPLE SIZE

No formal sample size was calculated, the sample size is based on empirical considerations. Considering a drop-out rate of 10% it is planned to randomize 66 patients overall (33 in each group) in order to ensure 60 evaluable patients overall (30 in each group) resulting in 180 unsupervised planned injections using SYDNEY, including the 2nd, 3rd and 4th unsupervised injections with SYDNEY for patients randomized in the AI group who will switch to SYDNEY group just before the second injection.

With 60 evaluable patients using SYDNEY, a total of 180 unsupervised injections is expected to be achieved during the study. Expecting a maximum of 3 observed PTC over the 180 injections (observed PTC rate of 1.67%) with SYDNEY, the upper bound of the 2-sided 95% confidence interval calculated with the Wilson score method will be no higher than 5.2%.

11.2 DISPOSITION OF PATIENTS

Screened patients are defined as any patient who met the inclusion criteria and none of the exclusion criteria, and signed the informed consent.

Randomized patients are all screened patients with a treatment kit number allocated and recorded in the IRT database, regardless of whether or not the treatment kit was used. These patients form the randomized population. Patients treated without being randomized will not be considered as randomized.

The safety experience of patients treated and not randomized will be reported separately, and these patients will not be included in the safety population.

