8.4 METHOD OF ASSIGNING PATIENTS TO TREATMENT GROUP

The randomized treatment kit number list is generated centrally by Sanofi. The IMPs are packaged in accordance with this list.

The trial Supply Operation Manager will provide the randomized list of treatment kit numbers and the Study Biostatistician will provide the randomization scheme to the centralized treatment allocation system provider. Then, this centralized treatment allocation system provider will generate the patient randomization list according to which it will allocate the treatment kits to the patients.

Patients will be randomized to receive either SYDNEY or AI for the first injection at Week 0 (on Day 1) using a ratio 1:1.

The treatment kit numbers will be allocated using the centralized treatment allocation system (IRT) on randomization visit Week 0 (Day 1), Week 4 (Day 29), Week 8 (Day 57) and Week 12 (Day 85).

Before randomizing a patient, the Investigator or designee will have to contact the centralized treatment allocation system (IRT).

A randomized patient is defined as a patient who is registered and assigned with a treatment kit number from the centralized treatment allocation system, as documented from its log file. A patient cannot be randomized more than once in the study. If a treatment is used without contacting the centralized treatment allocation system (IRT), the patient will be considered as not randomized and withdrawn from the study.

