11.3.2 Safety populations

The safety population of the parallel arms period will consist of all randomized patients who receive at least 1 dose or part of a dose of IMP during this period. Patient data will be analyzed according to the auto-injector device actually used.

The safety population of the single-arm period will consist of all randomized patients who continue in the single-arm period and receive at least 1 dose or part of a dose of IMP during this period.

All safety and PTC analyses will be performed on these populations.

In addition:

- Nonrandomized but treated patients will not be part of the safety population, but their safety data will be presented separately
- Randomized patients for whom it is unclear whether they took the IMP will be included in the safety population as randomized
- For a patient receiving injections with an auto-injector device different than the randomized auto-injector device during the parallel-arms period, the auto-injector device group allocation for as-treated analysis will be the auto-injector device actually used.

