2.2 DISPOSITION OF PATIENTS

This section describes patient disposition for both patient study status and the patient analysis populations.

Screened patients are defined as any patient who met the inclusion criteria and signed the informed consent.

Randomized patients consist of all screened patients with a treatment kit number allocated and recorded in the Interactive Response Technology database, regardless of whether the treatment kit was used. Patients treated without being randomized or treated with a double-blind treatment kit before the randomization will not be considered as randomized and will not be included in any analysis population. For patient study status, the following analyses will be performed in each period separately (by treatment group for parallel-arm period and overall for the single-arm period), if applicable:

- Screened patients
- Screen failure patients and reasons for screen failure
- Nonrandomized but treated patients (if any)
- Randomized patients
- Patients who completed the study treatment period as per protocol
- Patients who prematurely discontinued study treatment by main reason for permanent treatment discontinuation
- Status at last study contact (Alive/ Dead)

All critical or major deviations potentially impacting analyses, randomization, and drug-dispensing irregularities, and other major or critical deviations will be summarized in tables giving numbers and percentages of deviations by treatment group (when applicable).

Additionally, the following populations (for each study periods) will be summarized by treatment group for the populations of the parallel-arm period and overall for the populations of the single-arm period.

- Randomized population
- mITT population
- Safety population
- PKs population
- ADA population

Definitions of the study populations are provided in [Section 2.3](#).

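### Protocol 11.2 and SAP 2.2 make randomized patients a subset of an eligibility-based screened group, against protocol 8.4; read literally, some dosed but ineligible patients leave the analysis populations.

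*Protocol*

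**What the plan says.** Three places define who counts as randomized.

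- **Protocol 11.2.** "Screened patients are defined as any patient who met the inclusion criteria and none of the exclusion criteria, and signed the informed consent". The next definition builds on it: "Randomized patients are all screened patients with a treatment kit number allocated and recorded in the IRT database".
- **SAP 2.2.** "Screened patients are defined as any patient who met the inclusion criteria and signed the informed consent". The exclusion criteria are not mentioned. The nesting is the same: "Randomized patients consist of all screened patients with a treatment kit number allocated and recorded in the Interactive Response Technology database". SAP 1.5 reports no modification to the protocol's statistical section.
- **Protocol 8.4.** "A randomized patient is defined as a patient who is registered and assigned with a treatment kit number from the centralized treatment allocation system". This carries no eligibility condition and does not refer to screened patients.

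The populations in protocol 11.3 and SAP 2.3 all start from randomized patients. The population for the primary endpoint is an example: "The safety population of the single-arm period will consist of all randomized patients who continue in the single-arm period", with at least a partial dose in that period. Both documents report the safety of treated but non-randomized patients separately and keep those patients out of the safety population. SAP 2.2 also plans a disposition row, "Screen failure patients and reasons for screen failure", and a summary of critical or major deviations.

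**The concern.** Eligibility errors are sometimes found after dosing. If the definition of randomized depends on eligibility, finding such an error removes the patient from the analysis. That is a post-randomization exclusion in an open-label trial whose populations are otherwise described as as-randomized (mITT) or as-treated (safety, PK).

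At stake are the patient's unsupervised SYDNEY injections and any PTCs in the primary analysis, the adverse events in the main safety tables, and the LDL-C, PK and ADA data. The protocol and SAP would also give different denominators for the same patient. In the disposition table, a screened group made up only of eligible patients is the wrong denominator for screen failures.

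**Working it through.** **Step 1. Follow four kinds of patient through the three definitions.** Each patient has a kit allocated in the IRT and has been dosed.

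| Patient | Protocol 11.2 | SAP 2.2 | Protocol 8.4 |
|---|---|---|---|
| Meets all criteria | randomized | randomized | randomized |
| Breaches an exclusion criterion only (e.g. E 01, screening LDL-C below 70 mg/dL) | not randomized | randomized | randomized |
| Fails an inclusion criterion only | not randomized | not randomized | randomized |
| On a non-allowed statin dose since before screening (fails I 01, breaches E 02) | not randomized | not randomized | randomized |

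The rules agree only on the fully eligible patient.

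**Step 2. Compare with the SAP's own tables.** SAP 2.1.1 lists background statin at randomization with rows for atorvastatin 10 and 80 mg, rosuvastatin 5 and 40 mg, other doses and other statins. SAP 2.4.1 summarizes these on the randomized population. I 01 and E 02 allow only atorvastatin 20 or 40 mg and rosuvastatin 10 or 20 mg, and E 03 requires a stable dose up to randomization. Under protocol 11.2 the extra rows must be empty. Under SAP 2.2 they could hold only patients who met I 01 at screening and changed dose afterwards. The table layout and the deviation summary both suggest that ineligible patients are meant to stay in.

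**Step 3. Screen failures.** Under protocol 11.2 nobody who fails eligibility is screened. Under SAP 2.2 those breaching only an exclusion criterion are screened, but those failing an inclusion criterion are not. Protocol 10.1.1 and 10.1.2 require failures to be notified in the IRT, so counts and reasons exist. Only the label and denominator are wrong.

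**Step 4. Size for the primary endpoint.** Inputs from protocol 11.1: 60 evaluable patients, 3 unsupervised injections each (180), at most 3 PTCs, two-sided 95% Wilson interval.

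Upper bound = [p + z²/(2n) + z√(p(1−p)/n + z²/(4n²))] / (1 + z²/n), with z = 1.96.

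The plan's figure first. For 3/180, p = 0.01667, z²/(2n) = 0.01067, the square-root term times z is 0.02153, and the divisor is 1.02134. The upper bound is (0.01667 + 0.01067 + 0.02153)/1.02134 = 4.78%. With continuity correction it is 5.18%, which matches the stated limit of 5.2%.

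The documents give no rate of eligibility errors, so k ineligible patients is an assumption (1 to 3). Each removes up to 3 injections: n = 180 − 3k.

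| k | n | All 3 PTCs remain: rate, 95% CI | One PTC removed: rate, 95% CI |
|---|---|---|---|
| 0 | 180 | 1.67% (0.57–4.78) | – |
| 1 | 177 | 1.69% (0.58–4.86) | 1.13% (0.31–4.03) |
| 3 | 171 | 1.75% (0.60–5.03) | 1.17% (0.32–4.16) |

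With continuity correction, the upper bounds when all 3 PTCs remain are 5.18%, 5.27% and 5.45%.

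**Step 5. Which column is likelier.** If the 3 PTCs fall at random among 180 injections, the chance that at least one lies in the removed injections is 1 − (177·176·175)/(180·179·178) = 4.9% for k = 1, and 1 − (171·170·169)/(180·179·178) = 14.3% for k = 3. PTCs that cluster in patients who should not have been enrolled would raise these figures.

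**The case against.** The strongest reply is that no one would apply the definitions this way. Where the documents say who is not randomized, they name treatment without the IRT, or treatment without or before randomization. Ineligibility is never listed. Protocol 8.4 gives a clean operational rule. Eligibility is rechecked at Visit 2 (protocol 10.1.2), so few cases should arise. The primary endpoint is descriptive with no pass/fail threshold, so no conclusion turns on these shifts.

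Most of this stands as evidence of intent and of small size. It does not settle the text. Sections 11.2 and 2.2 define the randomized population, and a deviation summary does not restore anyone to it. The statin rows may also be a standard layout, so they suggest intent but do not prove it.

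Three stronger readings are tempting, and the documents do not support them:

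- **That any breach removes the patient under both documents.** Under SAP 2.2 only a failed inclusion criterion does so.
- **That the patient's safety data are lost.** Protocol 11.2 and 11.3.2 and SAP 2.3 and 2.3.2 have the safety of treated but non-randomized patients reported separately. The data leave the main tables only. That provision does not bring injections or PTCs back into the primary analysis.
- **That screen failures cannot be tabulated.** The IRT holds the notifications.

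**Conclusion.** The definitions are wrong as written and inconsistent across protocol 11.2, SAP 2.2 and protocol 8.4. Followed literally, protocol 11.2 removes every dosed patient who breached any criterion, and SAP 2.2 removes those who failed an inclusion criterion. Removal covers the primary PTC analysis, main safety, mITT, PK and ADA.

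The expected numerical effect is small and its direction is not fixed. Showing only the scenario in which a PTC disappears would mislead, because under random allocation the likelier result is a slightly higher upper bound. These figures rest on an assumed 1 to 3 ineligible patients, each contributing 3 injections, and on the planned 3 PTCs in 180. The case for change is the principle of not excluding dosed patients after randomization, and the need for one rule that a programmer can apply.

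**What to change.** In protocol 11.2 and SAP 2.2:

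1. Define screened patients as all who signed the informed consent.
2. Define screen failures as screened patients who were not randomized.
3. Define randomized patients as in protocol 8.4, with a kit number allocated and recorded in the IRT, and add that this holds regardless of eligibility.
4. State that eligibility breaches found after randomization are reported as deviations, and that these patients stay in each analysis population whose other conditions they meet.

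The cost is a few sentences in the SAP and matching protocol wording. No new data are needed, and the planned 60 evaluable patients and 180 injections do not change. If the protocol is not amended, SAP 1.5 should record the difference.

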11.3 ANALYSIS POPULATIONS

11.3.1 Modified intent-to-treat populations

The primary efficacy analysis population that will be used for the analyses of LDL-C will be the modified intent-to-treat (mITT) population.

The mITT population of the parallel arms period will consist of all randomized patients who receive at least 1 dose or part of a dose of IMP visit during this period and who had an evaluable value of LDL-C at baseline and an on-treatment LDL-C value within Week 4 analysis window. The treatment period for the parallel arms period is defined as the time period from the first IMP injection up to 35 days after this injection or up to the day before the second injection, whichever comes first. Patients in this mITT population will be analyzed according to the auto-injector device group allocated by randomization (ie, as-randomized treatment group).

The mITT population of the single-arm period will consist of all randomized patients who continue in single-arm period and receive at least 1 dose or part of a dose of IMP of this period and who had an evaluable value of LDL-C at baseline and at least one on-treatment LDL-C within one of the analysis windows from Week 8 to Week 16. The treatment period for the single-arm period is defined as the time period from the second IMP injection up to 35 days after the last IMP injection for patients entering into the single arm period.

11.3.2 Safety populations

The safety population of the parallel arms period will consist of all randomized patients who receive at least 1 dose or part of a dose of IMP during this period. Patient data will be analyzed according to the auto-injector device actually used.

The safety population of the single-arm period will consist of all randomized patients who continue in the single-arm period and receive at least 1 dose or part of a dose of IMP during this period.

All safety and PTC analyses will be performed on these populations.

In addition:

- Nonrandomized but treated patients will not be part of the safety population, but their safety data will be presented separately
- Randomized patients for whom it is unclear whether they took the IMP will be included in the safety population as randomized
- For a patient receiving injections with an auto-injector device different than the randomized auto-injector device during the parallel-arms period, the auto-injector device group allocation for as-treated analysis will be the auto-injector device actually used.

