8.5 PACKAGING AND LABELING

The treatment kit with AI will be prepared to contain 2 auto-injectors (2 x 1 mL) whereas the treatment kit with SYDNEY will be prepared to contain 1 auto-injector (1 x 2 mL).

In addition to the open-label treatment kits, a dummy kit for practice containing 1 auto-injector each will be prepared for the purpose of instructing patients on injection administration which is to be performed prior to randomization. These training injections will be performed on site at randomization Week 0 (Visit 2, Day1).

Packaging is in accordance with the administration schedule. The content of the labeling is in accordance with the local regulatory specifications and requirements.

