2.1.3 Primary endpoint

The primary endpoint is the number (%) and types of SYDNEY-associated PTCs at the unsupervised injections on Weeks 4, 8, and 12. In this study, a PTC is defined as any complaint reported on the Patient Complaint form that triggered an investigation by the Device Department and was classified by this department as device-related, patient-related, or undetermined, whether or not associated with an AE. The complaints categorized as not related to device or patient will not be considered as a PTC. This definition will be used for both primary and secondary endpoints.

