2.1.4 Secondary endpoints

2.1.4.1 Device-related endpoints

During the parallel-arm period, patients are to receive injection(s) with either SYDNEY device or current AI. During the single arm period, all patients are to receive 3 separate injections with the SYDNEY device only.

The following endpoints will be analyzed:

- For both devices:
 - Number and percentage of patients with SYDNEY or current AI- associated PTCs (overall and by type) at the supervised injections on Day 1
 - Injection experience questionnaire on Day 1
- For SYDNEY only:
 - Number and percentage of patients with a SYDNEY- associated PTC (overall and by type) at the unsupervised injections on Weeks 4, 8, and 12
 - Patient perspective questionnaire
 - Injection-Treatment Acceptance Questionnaire

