2.3.2 Safety population

The safety population of the parallel arms period will consist of all randomized patients who received at least 1 dose or part of a dose of IMP during this period. Patient data will be analyzed according to the auto-injector device actually used.

The safety population of the single-arm period will consist of all randomized patients who continued in the single-arm period and receive at least 1 dose or part of a dose of IMP during this period.

All safety and PTC analyses will be performed on these populations.

In addition:

- Nonrandomized but treated patients (if any) will not be part of the safety population, but their safety data will be presented separately.
- Randomized patients for whom it is unclear whether they took the IMP will be included in the safety population as randomized.

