2.4.4.2 Analysis of secondary endpoints

2.4.4.2.1 Device-related endpoints

All secondary device-related endpoints will be analyzed on the safety population using descriptive statistics. In addition, 95% CI for the number of PTCs, number and % of patients with any PTCs will be provided using Wilson score method.

Questionnaires will be analyzed with descriptive statistics.

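### A Day 1 SYDNEY known to have delivered nothing, with no working replacement used, takes its own complaint out of the descriptive Day 1 PTC percentage

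*Protocol*

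**What the plan says.** - **Analysis set.** Under SAP 2.3.2 the "safety population of the parallel arms period will consist of all randomized patients who received at least 1 dose or part of a dose" in that period; Protocol 11.3.2 sets the same condition. On PTCs, Protocol 11.3.2 adds: "All safety and PTC analyses will be performed on these populations". The SAP repeats this.
- **The one relaxation.** Protocol 11.3.2: "Randomized patients for whom it is unclear whether they took the IMP will be included in the safety population as randomized". The SAP carries the same clause.
- **What a PTC is.** SAP 2.1.3 (and Protocol 9.1) starts from "any complaint reported on the Patient Complaint form that triggered an investigation by the Device Department" and then requires that it be classed as device-related, patient-related or undetermined. Delivery of drug is not part of the definition.
- **Affected endpoint.** SAP 2.1.4.1 lists "Number and percentage of patients with SYDNEY or current AI- associated PTCs (overall and by type) at the supervised injections on Day 1". SAP 2.4.4.2.1 analyses it descriptively on the safety population and adds that "95% CI for the number of PTCs, number and % of patients with any PTCs will be provided using Wilson score method".
- **Devices per dose.** Under Protocol 8.5 the AI kit is to "contain 2 auto-injectors (2 x 1 mL) whereas the treatment kit with SYDNEY will be prepared to contain 1 auto-injector (1 x 2 mL").
- **Where the loss would show.** SAP 2.2 says "the following populations (for each study periods) will be summarized by treatment group for the populations of the parallel-arm period"; the list includes the randomized and the safety populations. SAP 2.4.4.1, on the primary endpoint, also has every reported complaint described, whether or not it was confirmed as a PTC.

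**The concern.** Receiving drug is a sensible entry condition for adverse event tables. For a device endpoint it is awkward, because failure to deliver is itself one of the outcomes of interest. Under the stated rule the most complete kind of failure can remove both the patient from the denominator and the complaint from the numerator.

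At stake is the Day 1 PTC percentage, which serves the secondary objective of assessing robustness and user interaction of both devices under supervision (Protocol 5.2). The scenario is foreseeable. SYDNEY is single-use and self-disabling (Protocol 8.1.1.2). Protocol 8.1.2 anticipates that some patients may have trouble activating an auto-injector. A use error that loses the whole dose can also be a PTC, because patient-related complaints count.

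**Working it through.** **1. Inputs.** 33 patients randomized per arm; at most 3 PTCs expected in 180 unsupervised injections, with a stated Wilson upper bound no higher than 5.2% (Protocol 11.1, SAP 1.3); one SYDNEY or two AI devices per dose (Protocol 8.5).

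**2. The plan's own figure.** Wilson limits, with z = 1.96:

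(p + z²/2n ± z·√[p(1−p)/n + z²/4n²]) / (1 + z²/n)

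For 3/180 this gives 0.57% to 4.78%. With a continuity correction it gives 0.43% to 5.18%, which is the stated 5.2%. The figure is therefore reproduced by the continuity-corrected form, and the plain form also lies below it. It rests on 180 single-arm injections, so the Day 1 issue does not touch it.

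**3. Who is dropped on Day 1.**

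| Day 1 event, no working replacement used | Part of a dose received? | In the Day 1 PTC table? |
|---|---|---|
| SYDNEY delivers part of its dose | Yes | Yes |
| SYDNEY, unclear whether anything was delivered | Unclear | Yes, by the relaxation clause |
| SYDNEY known to deliver nothing | No | **No** |
| One AI of two delivers nothing, the other works | Yes | Yes |
| Both AI known to deliver nothing | No | **No** |

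The rule is the same for both devices. The difference between them is one of degree, because it takes one failure to drop a SYDNEY patient and two to drop an AI patient. A successful injection at Week 4 brings the patient into the single-arm population but not back into the Day 1 table.

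**4. Size if it happens once among 33 SYDNEY patients (plain Wilson).**

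- Attempt counted: 1/33 = 3.03%. Centre (0.0303 + 0.0582)/1.1164 = 0.0793, half-width 0.0739, so 0.5% to 15.3%.
- As written: 0/32 = 0%. Upper limit z²/(n + z²) = 3.84/35.84, so 0 to 10.7%.
- With one other SYDNEY PTC in a dosed patient: 2/33 = 6.1% (1.7 to 19.6%) becomes 1/32 = 3.1% (0.6 to 15.7%).
- With the continuity correction, the first pair is 0.2 to 17.5% against 0 to 13.3%.

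**5. How often.** The documents give no complete-failure rate, so q per device is an assumption. Expected SYDNEY exclusions are 33q. The chance of at least one is 1 − (1 − q)^33 for SYDNEY, and 1 − (1 − q²)^33 for AI if a patient's two devices fail independently.

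| Assumed q | Expected SYDNEY exclusions | At least one, SYDNEY | At least one, AI (independent) |
|---|---|---|---|
| 0.1% | 0.03 | 3.2% | 0.003% |
| 0.5% | 0.17 | 15.2% | 0.08% |
| 1% | 0.33 | 28% | 0.3% |
| 1.67% | 0.55 | 43% | 0.9% |

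The last row borrows the planning maximum of 3/180. That maximum covers all PTC types at unsupervised injections, so complete failures would be only a part of it. If a patient's two AI devices always fail together, the AI chance equals that for SYDNEY.

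**6. Primary rate.** A patient with a failed injection at Week 4, 8 or 12 stays in the single-arm population if any other injection in that period delivers part of a dose. The complaint is lost only when nothing at all is delivered in the period.

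**The case against.** The case against is substantial.

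- **Stacked conditions.** The failure must occur on Day 1, deliver nothing, be known to have delivered nothing, and be followed by no working replacement. Day 1 is on site, supervised and preceded by training on both devices. A replacement used in the period would bring patient and complaint back in. This stands, and it is why the frequency is left open.
- **The clause for unclear dosing.** No delivered volume is measured, so some zero-delivery cases would count as unclear and stay in. This also stands, but site staff watching the injection could see an obvious non-delivery, and the clause does not cover that.
- **The event is not hidden.** The complaint and device go for investigation whatever was delivered (Protocol 6.1, 10.4.5), all complaints are described, and a safety population of 32 would stand beside 33 randomized. This is correct as far as it goes. However, randomized patients include those whose kit was never used (Protocol 11.2), so the count does not identify a device failure. Neither safeguard restores the event to the Day 1 percentage.

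A reader might infer that the rule tilts a SYDNEY-versus-AI comparison. The documents do not support that: Protocol 4.2.2 plans a two-device comparison for PK/PD and safety, not PTCs, and the Day 1 table carries no test. Nor do they support the inference that failures are concealed from the report.

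**Conclusion.** The point holds in a narrow form and is minor. It follows from the stated rule that a Day 1 SYDNEY known to have delivered nothing, with no working replacement used, is left out of the Day 1 PTC percentage and interval. One such case moves the percentage by about 3 points, and with no other PTC the table would show zero. The conclusion rests on reading the dose condition as written and on the documents' silence about replacement. The rates in the frequency table are assumptions.

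A reader might go further and infer that the primary PTC rate is understated. The text does not support a material effect there, because loss requires a patient with no delivery at all in the single-arm period.

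**What to change.** For PTC endpoints only, define the analysis set as follows: the safety population of the period, keeping patients whose dosing is uncertain, plus any randomized patient in whom use of a dispensed study device was started or attempted in that period. This includes a device found unusable during preparation, applies whether or not drug was delivered, and groups patients by the device actually used. Put the definition in Protocol 11.3.2 and SAP 2.3.2, and refer to it in SAP 2.4.4.1 and 2.4.4.2.1. Keep the present safety population for adverse events.

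Building on the safety population preserves the existing rule for uncertain dosing. Naming preparation matters because a complaint about the device or the injection process is reportable (Protocol 10.4.5) even when no injection was attempted.

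Identify the added patients from the Patient Complaint form, the returned device, the diary or the e-CRF, and confirm before database lock that an attempt without delivery is captured. The documents do not show that it is. Diaries are completed after a self-injection has been performed (Protocol 9.1), and only Week 12 has an explicit e-CRF item on whether the full injection was done (Protocol 10.1.6).

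The cost is one definition, four cross-references, one data-source check and possibly one e-CRF item. The PTC percentage may come out slightly less favourable.
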